4.1 Study overview

Subjects will be recruited through protocol number 13-N-0149 (ALL HANDS protocol, PI [name]), other IRB-approved intramural NIH protocols, or through referrals from outside providers/institutions or self-referred. Participants will be evaluated for eligibility to one of the groups (A-E). Once consented and found eligible, subjects will undergo PET scanning using 18F-FDOPA and/or 11C-DASB. All the visits will be on outpatient basis unless a participant is inpatient at the Clinical Center for another protocol. There will be no follow-up visits after the completion of the PET scan(s). In case the planned scans cannot be done for any reason and the subject is still eligible and willing to participate, a second visit will be scheduled to complete the study procedures.

4.2 Recruitment

Subjects will be recruited through protocol number 13-N-0149 (ALL HANDS protocol, PI [name]), through other IRB-approved intramural NIH protocols, through referrals from outside providers/institutions or through self-referral.

We will send an IRB approved letter to the PIs of NIH protocols targeting HIV infected subjects (Appendix B) and ask for help in identifying potential subjects in their protocols who might be interested in our study. We will also include an IRB approved flyer describing our study to give to volunteers. If the subjects express interest, we will access their medical record at NIH to evaluate if they are potentially eligible. We will then proceed to contact them for more information as below.

If we get referrals from outside providers/institutions or self-referred potential subjects contact us, we will conduct a phone interview and ask them to send us relevant medical records to evaluate if they satisfy the eligibility criteria.

When a subject (either referred from an NIH protocol, from outside providers/institutions or self-referred) is evaluated and found to be potentially eligible based on the inclusion/exclusion criteria of one or more of the groups, he/she will be re-contacted

about participating in one or more of our PET studies. If the subject is at NIH, the investigators will explain the nature of the study with all the associated risks in person. If they are not at NIH, investigators will call the subject to explain the nature of the study with all the associated risks. If the subjects are still interested in participating, they will be asked to sign the informed consent document before any study procedures are conducted and they will be scheduled for screening procedures to evaluate if they are eligible. For NIH employees, there will be no direct solicitation of employees/staff by supervisors.

4.3 Schedule of Activities (SOA)

Procedures	Time Point ^a		
	Screening	Visit 1	Visit 2
Informed consent	X		
Demographics	X		
Medical history	X		
Physical exam and vital signs	X		
Client Diagnostic Questionnaire (CDQ)	X		
Laboratory Tests ^b	X		
Urine toxicology screen ^c	X	X	
Pregnancy test ^c		X	
Neuropsychological testing ^d			X
MRI (Brain)	X		
PET (18F-FDOPA and/or 11C-DASB) ^e		X	
Adverse event review and evaluation			X

^a If not all procedures could be completed in one visit, they could be rescheduled to another day.
^b HIV RNA Viral Load (only for groups A and D)), CBC/diff/platelets, hepatic panel, Hemoglobin A1c (if known history of Diabetes mellitus), fasting lipid profile, Acute Care Panel, Hep C antibody and HCV RNA Quant) (No need to be performed if its performed within 3 month of planned PET scan)
^c Urine toxicology and urine or serum pregnancy test will be performed 48 hours or less prior to the planned scan and must be checked before scanning.
^d Neuropsychological test may include the following: WTAR; WAIS-III; TMT; HVLT-R; BVMT-R; WCST-64; COWAT; FAS and Animals; PASAT; Grooved Pegboard Test; Judgment of Line Orientation and Medical Symptom Validity Test.
^e The PET (18F-FDOPA and/or 11C-DASB) scanning will be performed either on the same day (one visit) or on two separate visits based on the subject's preferences and scan time availability.

4.4 Screening

4.4.1 Screening activities performed prior to obtaining informed consent

Minimal risk activities that may be performed before the subject has signed a consent include the following:

- Email, written, in person or telephone communications with prospective subjects.
- Review of existing medical records to include H&P, laboratory studies, etc.

- Review of existing brain MRI images.

Since this study was approved before revised Common Rule that did not allow pre-screening procedures without the consent, it is being requested that consent for pre-screening procedures be waived

4.4.2 Screening activities performed after a consent for screening has been signed

The evaluations will be completed at the National Institutes of Health (NIH) Clinical Center. We will obtain informed consent before any screening procedures. The following procedures will be performed for screening purposes:

- History and physical exam including vital signs (No need to be repeated if it has been performed at NIH within 3 month of planned PET scan)
- Laboratory tests: HIV RNA Viral Load (only for groups A and D), CBC/diff/platelets, hepatic panel, Hemoglobin A1c (if known history of Diabetes mellitus), fasting lipid profile, Acute Care Panel, Hep C antibody and HCV RNA Quant). (No need to be repeated if performed at NIH within 3 month of planned PET scan)
- MRI Brain (No need to be repeated if performed at NIH within one year of planned PET scan)
- Client diagnostic test (CDQ) (No need to be repeated if performed at NIH within 3 months of planned PET scan)

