3.2.3 HIV-negative Subjects WITH Co-morbidities (Group B, n=25)

1. HIV-antibody negative
2. At least one or more of the following criteria:
 - a. Hypertension, as defined by treatment with medications for hypertension or with a systolic blood pressure at screening ≥ 140 mm Hg.
 - b. Diabetes mellitus, as defined by HgbA1C $\geq 6.5\%$ or known treatment for diabetes.
 - c. Hepatitis C infection as documented by lab results of a positive Hepatitis C antibody and/or detectable Hepatitis C viral load. Subjects who responded to HCV treatment (SVR) will be included.
 - d. History of previous but not current drug abuse
 - e. History of previous but not current alcoholism (defined as alcohol intake that affect/affected the subject's work or home life).
 - f. Clinical atherosclerotic cardiovascular disease (ASCVD) (e.g. history of acute coronary syndromes, or myocardial infarction, stable or unstable angina, coronary or other arterial revascularization or peripheral arterial disease of atherosclerotic origin) and/or 10-year heart disease risk score (ASCVD risk score) $>7.5\%$ (7.5 % score is the threshold for starting statin therapy as per the 2013 American College of Cardiology [ACC] / American Heart Association [AHA] guidelines ³³).

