3.2.4 HIV-negative Subjects WITHOUT co-morbidities (Group C, n=25)

1. HIV-antibody negative
2. No history of any of the following:
 - a. Hypertension, as defined by treatment with medications for hypertension or with a systolic blood pressure at screening ≥ 140 mm Hg.
 - b. Diabetes mellitus, as defined HgbA1C $\geq 6.5\%$ or treatment for diabetes.
 - c. Hepatitis C infection as documented by lab results of positive Hepatitis C antibody and/or detectable Hepatitis C viral load. Subjects who responded to HCV treatment (SVR) will not be included.

- d. History of previous drug abuse.
- e. History of previous alcoholism. Alcoholism is based on alcohol having affected the subject's work or home life.
- f. Clinical ASCVD (e.g. history of acute coronary syndromes, or myocardial infarction, stable or unstable angina, coronary or other arterial revascularization or peripheral arterial disease of atherosclerotic origin) and/or 10-year heart disease risk score (ASCVD risk score) >7.5% (7.5 % score is the threshold for starting statin therapy as per the 2013 ACC/AHA guidelines ³³).
- g. Any other disease entities including chronic infections (e.g. Hepatitis B, Lyme disease), neurological diseases (e.g. Multiple sclerosis, vasculitis) or systemic diseases (e.g. Sjogren's diseases, sarcoidosis, systemic lupus erythematosus [SLE]) that in the opinion of the investigator would be considered a significant co-morbidity.

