4.5 Study Procedures

4.5.1 Clinical Evaluations

An interim medical history (including antiretroviral adherence) and assessment of vital signs will be performed within 48 hours of the scan. If in the assessment of the investigator, there are interim findings that could impact selection group criteria (e.g. change in medications or new symptoms), additional screening lab work may be ordered and scanning will be not be performed until the results are back. Abnormal results will be communicated to subjects.

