13.2 Consent procedures

All volunteers will receive a verbal explanation in terms suited to their comprehension of the purposes, procedures and potential risks of the study and of their rights as research volunteers. Participants will have the opportunity to carefully review the written consent form and ask questions regarding this study prior to signing. The investigator obtaining consent will document the consent process in the participant's medical record. A copy of the completed signed informed consent form will be provided to the participant.

Loss of consent capacity during participation is unlikely, so a durable power of attorney will not be required. If loss of consent capacity occurs during the study, the subject will be excluded/taken off study.

In most cases, it is clear whether subjects are competent to make their own decisions, and this can be judged by the evaluating physician. Occasionally, it is not so clear. In those cases, the subject is considered able to provide informed consent if he/she:

- Understands his or her situation/medical condition.
- Understands the risks associated with the research.
- Communicates a decision based on that understanding.

If after this assessment, there is still doubt about the subject's competency to provide informed consent, we will consult the Clinical Center Capacity Assessment Team (ACAT) before enrolling the subject. Individuals who are unable to consent are not eligible for initial enrollment.

The subjects will sign the informed consent document prior to undergoing any research procedures. The subjects may withdraw consent at any time throughout the course of the study. The rights and welfare of the subjects will be protected by emphasizing to the

subjects that the quality of their medical care will not be adversely affected if they decline to participate in this study.

Prior to the scheduled PET scans, subjects will undergo a focused short assessment to confirm no change in eligibility criteria and to rule out the possibility of pregnancy despite a negative pregnancy test.

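### Screening does not order HbA1c for the Group C candidates it would reclassify; separately, the viral-load eligibility limit appears to be printed in the wrong unit

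*Combined protocol and SAP*

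**What the plan says.** **Group definitions.** Section 3.2.3 admits an HIV-negative subject to Group B on any one listed co-morbidity. One of these is "Diabetes mellitus, as defined by HgbA1C" of at least 6.5%, or known treatment. Section 3.2.4 requires Group C to have no history of the same list, including "Diabetes mellitus, as defined HgbA1C" at the same threshold, or treatment.

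**What is measured.** Section 4.4.2 lists the screening blood work as including "Hemoglobin A1c (if known history of Diabetes mellitus), fasting lipid profile, Acute Care Panel, Hep C antibody and HCV RNA Quant". Footnote b of the schedule in section 4.3 carries the same condition: "hepatic panel, Hemoglobin A1c (if known history of Diabetes mellitus". Results up to three months old may be carried over.

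**Other routes before the scan.**
- Section 4.4.1 permits, before consent, "Review of existing medical records to include H&P, laboratory studies, etc". Section 4.2 adds that NIH records will be accessed and outside records requested.
- Section 4.5.1 applies where "there are interim findings that could impact selection group criteria (e.g. change in medications or new symptoms"; then "additional screening lab work may be ordered and scanning will be not be performed until the results are back".
- Section 13.2 says that before scanning "subjects will undergo a focused short assessment to confirm no change in eligibility criteria".

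**After the scan.** Section 4.1 provides no follow-up visit, and section 5.1 provides no stored blood.

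**Viral load.** Section 3.1 describes the HIV-positive subjects as having plasma HIV-RNA under 100 copies/mm³ or below detection (BLD) for more than a year. Section 3.2.2 requires BLD, with under 100 copies/mm³ in brackets. Section 2.1 calls the population virologically controlled.

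**The concern.** **HbA1c.** Someone who appears to belong in Group C has, by construction, no known diabetes, so the test is never triggered for that person. The laboratory half of the definition is switched off for the only people it could move from C to B. The other measurable criteria are not conditional in this way: blood pressure, hepatitis C serology and RNA, and lipids are planned for everyone. Group C is the co-morbidity-free reference in the dopaminergic arm, and the B/C split supports the secondary objective of separating HIV damage from co-morbidity damage. A misplaced subject would tend to pull C towards B, and nothing after the scan could reveal it.

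**Viral load.** This is an eligibility limit for every HIV-positive subject in both arms. Section 1.2 sets this study apart from earlier dopaminergic PET work because some of those subjects were viremic. It also cites a correlation between higher plasma viral load and lower transporter availability in HIV dementia. Read literally, the printed limit would admit the kind of subject the study means to leave out.

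**Working it through.** **1. Can the plan, followed exactly, miss an HbA1c of at least 6.5% in Group C?**

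Take a candidate with untreated, unrecognised diabetes, no other listed co-morbidity and no HbA1c on record.
- The screening list (4.3 footnote b, 4.4.2) orders no HbA1c, because diabetes is not known.
- Record review (4.2, 4.4.1) can find only a value that already exists.
- Extra laboratory work (4.5.1) is optional and needs an interim finding to prompt it.
- The pre-scan check (13.2) looks for change, so it cannot detect a value never measured.

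The candidate can enter Group C. Under 3.2.3 the same person belongs in Group B.

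**2. The plan's own sample size**

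Inputs from section 10.1 (caudate Ki):

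| Group | Mean | SD |
|---|---|---|
| A (HIV-positive) | 0.008833 | 0.001358 |
| B (HIV-negative, co-morbid; assumed mid-point) | 0.0100665 | 0.001539 |
| C (healthy controls) | 0.0113 | 0.0017 |

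Alpha is 0.05, taken as two-sided. The power formula is the two-sample noncentral t with SD s = √((s₁² + s₂²)/2), noncentrality = difference / (s√(2/n)) and 2n − 2 degrees of freedom.

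A versus B: difference 0.0100665 − 0.008833 = 0.0012335; s = 0.0014513.
- n = 22: power 78.6%.
- n = 23: noncentrality 0.0012335/0.00042797 = 2.882; power 80.5%. This reproduces the plan's 23 per group.
- n = 25: noncentrality 0.0012335/0.00041050 = 3.005; power 83.8%.

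**3. Illustration of misclassification in Group C**

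The documents give no rate of unrecognised diabetes and no link from it to caudate Ki. Assume that k of the 25 Group C subjects are misclassified, with their mean Ki anywhere from C's mean (no effect) to B's mean. SDs are held constant.

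B versus C: s = √((0.001539² + 0.0017²)/2) = 0.0016215; standard error = 0.0016215 × √(2/25) = 0.00045863. With misclassified subjects at B's mean, the difference is 0.0012335 × (1 − k/25).

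| k | Difference | Noncentrality | Power, at B's mean | Power, halfway | Power, at C's mean |
|---|---|---|---|---|---|
| 0 | 0.0012335 | 2.690 | 75.0% | 75.0% | 75.0% |
| 1 | 0.0011842 | 2.582 | 71.6% | 73.3% | 75.0% |
| 2 | 0.0011348 | 2.474 | 67.9% | 71.6% | 75.0% |

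The other contrasts at 25 per group, with misclassified subjects at B's mean:
- A versus B uses no Group C data: 83.8% for any k.
- A versus C: 99.98%, 99.98% and 99.96% for k = 0, 1, 2.
- Omnibus ANOVA (noncentral F, 2 and 72 df, pooled SD 0.0015387): 99.94%, 99.91% and 99.87%.

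**4. The viral-load unit**

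1 mL = 1,000 mm³, so 100 copies/mm³ = 100 × 1,000 = 100,000 copies/mL. The factor between the two units is 1,000. A limit of 100,000 copies/mL does not fit BLD or the reference to a suppressed viral load in 3.2.2, or virological control in 2.1. The two sections also differ in logic: 3.2.2 equates the number with BLD, while 3.1 makes it an alternative. The limit governs 25 + 20 = 45 target places (Groups A and D).

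**The case against.** **The no-history wording.** Section 3.2.4 could be read as excluding known diabetes only, so that ordering HbA1c on history would be consistent. This does not hold up. The criterion is defined by a laboratory threshold, and the same list counts a systolic pressure measured at screening, so new measurements are meant to count.

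**Other safeguards.** Screening includes a history and physical examination and an Acute Care Panel whose contents are not stated, so it may include glucose. The payment table also allows for second-visit blood tests if needed. These make a missed case less likely, but none requires an HbA1c value.

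**The effect is minor.** This stands. The plan sets no power target for B versus C, and one or two misclassified subjects is an arbitrary choice. Nor is the range a strict bound. Allowing for the extra variance of a mixed group lowers the worst cases to 71.3% and 67.3%, a change of at most 0.6 points, and a misclassified subject could lie beyond B's assumed mean. The point rests on the definition not being applied, and the power figures only give it scale.

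**The unit is probably a typing error.** The operative criterion in 3.2.2 names BLD, which a viremic subject would fail whatever the unit. That makes literal use unlikely. But 3.1 offers the number as an alternative to BLD, and the documents give no assay limit from which to infer the intended figure.

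**The two points are unrelated.** They are, and each should be judged separately. Both are eligibility details that can be corrected in one amendment.

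**Conclusion.** Both points hold.

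**HbA1c.** One of the criteria that define Group C is not measured in the people it is meant to exclude. The likely effect is small and cannot be quantified from the documents. In the illustration, B-versus-C power falls from 75.0% to no lower than 71.6% with one misclassified subject, or 67.9% with two. This assumes section 10.1's caudate Ki values, constant SDs, and misclassified subjects no further from C than B's assumed mean. A versus B, which sized the study, is unaffected, and A versus C and the omnibus test barely move. Group E is not involved because it accepts subjects with or without co-morbidities.

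**Viral load.** The limit appears wrong as written, by a factor of 1,000 if per mL was meant. The documents do not establish what was intended, and no power effect is claimed.

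Both should be corrected; neither undermines the main comparison. Confidence is medium.

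**What to change.** **HbA1c.** In footnote b of section 4.3 and in section 4.4.2, order HbA1c on the screening blood for every HIV-negative dopaminergic-arm candidate who would otherwise enter Group C, with the same three-month carry-over. Candidates already in Group B through another criterion do not need it for classification. Rewording the criterion as known diabetes would also remove the inconsistency, but it would weaken what Group C stands for.

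The cost is one routine assay in about 25 candidates at target. It rises to 35 if all 10 extra HIV-negative places under the accrual ceiling (60 − 50) went to Group C, which is an assumption because section 3.1 does not divide the ceiling between B and C. Screen failures would add a few, and a new draw is needed where carried-over results lack HbA1c.

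**Viral load.** The sponsor should confirm the intended limit, state it in the unit the assay reports, and use the same wording in 3.1 and 3.2.2, including whether the number defines BLD or is an alternative to it. Once confirmed, this is a text correction.

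Neither change alters a planned sample size.

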4.4.2.1 Client Diagnostic Test (CDQ)

Psychiatric disorders and substance use disorders will be assessed with the Client Diagnostic Questionnaire (CDQ)⁴¹, a psychiatric screening tool that was adapted from the PRIME-MD⁴²a well-validated screening tool for assessing psychiatric disorders and substance use disorders in primary care settings. The CDQ was developed and validated for persons affected by HIV. For the diagnosis of any disorder, the sensitivity, specificity, overall accuracy, and kappa coefficient of the CDQ were 91%, 78%, 85% and 70%, respectively. We will use the CDQ to screen for presence of major depressive disorder, other depressive disorder, panic disorder, generalized anxiety disorder, post-traumatic stress disorder (PTSD), psychosis, alcohol abuse and substance abuse. If during the CDQ, we identify evidence of severe depression (“I would like to kill myself” or “I would kill myself if I had a chance”), a psychiatric consult will automatically be offered to the subject with the goal to assess his or her immediate safety. The role of this psychiatry consult is only to assess and manage immediate safety concerns, and not to provide an ongoing mental health treatment. However, in each case where the psychiatrist or psychologist, following the safety assessment, recommends mental health treatment, the participant will be advised to pursue the recommended treatment outside of the clinical center and according to her/his healthcare access plan.

4.4.2.2 MRI brain

Subjects will undergo a 3 tesla MRI scan of the brain for research purposes and to evaluate anatomical abnormalities. This scan may also be used for localization of PET regions for other studies of HIV-HAND planning to use PET. MRI scanning will be performed at the NIH Clinical Center or the NMR Center, and the procedure takes about 1-2 hours. Persons requiring more than oral lorazepam (or an equivalent) as sedation for MRI will be excluded from the protocol.

The imaging protocol may include:

2. Basic anatomical imaging sequences, including but not limited to PD/T2-weighted images as well as unenhanced T1, T2*, and FLAIR images.
3. Diffusion weighted imaging.
4. 3D T1weighted images, which will be used for co-registration with the PET.

Interpretation of imaging studies: All structural MR images of the brain will be interpreted qualitatively by the neuroradiologist on call as soon as possible after the completion of the scan. During scanning, the images will be monitored for quality (e.g., motion artifacts degrading the images) and repeated as needed. Coregistration of 3D T1 weighted images with the PET images will be performed later on a specialized workstation connected to the PACS system in Radiology/nuclear medicine. The MRI imaging will be used to rule out major acute abnormalities that need immediate clinical attention, or subacute/chronic conditions that require further medical care. This information will be shared with the subject and his/her primary doctor. If needed, the subject will also be referred to his/her primary doctor for further evaluations and treatment. If the subject does not have insurance or primary care physician, the study team will assist him/her in finding medical care.

MRI scans are performed on FDA-approved scanners with FDA-approved radiofrequency coils and FDA-approved pulse sequences, and their use conforms to the corresponding FDA labels. Acquisition parameters may be modified within the permitted range. These studies may involve software modifications as allowed under 21 CFR 812.2(b)(4), which stipulates that any modification “is not for the purpose of determining safety or effectiveness and does not put subjects at risk.” All research pulse sequences will not conform to the FDA’s Criteria for Significant Risk Investigations of Magnetic Resonance Diagnostic Devices.

We use MR Image Reconstruction and Analysis Software, this software is provided/developed by Pmod (Zurich, Switzerland). We use Pmod to reconstruct MRI imaging and co-register MRI to PET scans acquired in this study. This software is used for research purposes only and not intended for use for clinical diagnosis or direct clinical efficacy testing. We classify the software as an NSR device under this protocol. For the purposes of this protocol, research post processing software is exempt from the IDE regulations under 21 CFR 812.2(c) because it is noninvasive, does not require an invasive sampling procedure that presents significant risk, and does not by design or intention introduce energy into a subject.

